6 STUDY ASSESSMENTS

6.1 Safety assessments

6.1.1 Adverse Event Assessments

Information regarding occurrence of AEs will be captured throughout the study. The study site visits are designed to ensure any untoward events in subjects are quickly identified by the investigator and can be treated promptly. Duration (start and stop dates), severity/grade, outcome, treatment and relationship to study medication will be recorded.

6.1.2 Clinical Laboratory Evaluations

Non-fasting samples for clinical laboratory analysis will be collected by a qualified investigational center staff member at Visits 1, 2 (prior to the randomization) and 5 (prior to the study medication application at the visit). The following tests, at a minimum, will be conducted:

Chemistry Panel	Complete Blood Count
Albumin	Hematocrit
Alkaline phosphatase	Hemoglobin
Alanine aminotransferase (ALT)	Platelet count
Aspartate aminotransferase (AST)	Red blood cell morphology
Blood urea nitrogen (BUN)	Red blood cell count
Bicarbonate	White blood cell count
Calcium	White blood cell differential
Chloride	% & absolute
Creatinine	Basophils
Glucose	Eosinophils
Lactate dehydrogenase (LDH)	Lymphocytes
Phosphorus	Monocytes
Potassium	Neutrophils
Sodium	-
Total bilirubin	Urinalysis with Microscopic
Total protein	•
Uric acid	

The results of the clinical laboratory tests will be reported on the laboratory's standard reports. The investigator must note NCR or clinically relevant (CR) to define the clinical relevance of any result that is outside the normal range for the laboratory. The investigator must date and sign/initial every laboratory report.

The investigator must review each subject's Visit 1 laboratory reports prior to Visit 2. The subject must not be randomized if any of the Visit 1 results are outside normal range for the laboratory AND, in the opinion of the investigator, CR. The investigator must review all laboratory reports in a timely manner.

The investigator must report all laboratory results that are BOTH outside the normal range for the laboratory AND, in the opinion of the investigator, CR as medical history if found prior to the first study medication application or as an AE if found after the first study medication application begins.

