The third and fourth secondary objectives are to determine the clinical efficacy of NFX-179 Gel defined as the change from baseline in the Subject's Self-Assessment grade and Physician's Tumor Assessment grade, separately, after 28 days of treatment. Appropriate mixed-model ANCOVAs will be used to compare, for each treated tumor, change from baseline grade between treatment groups, with treatment as the independent factor, baseline value as the covariate, and subject as the repeated factor. ANCOVA models will also be performed on the subject level after first calculating the within-subject mean values across treated tumors. In addition, for each assessment dichotomized analyses will be conducted on the proportion of tumors achieving a grade of Clear, and also the proportion of tumors achieving a grade of either Clear or Almost Clear, after 28 days of treatment. Treatment groups will be compared to vehicle using appropriate mixed-model logistic regression, as well as a Chisquare analysis of within-subject averaged results across tumors.

Safety Analyses:

Subjects will be assessed for the occurrence of new and ongoing AEs. Descriptions of AEs will include the dates of onset and resolution (if resolved), maximum severity, seriousness, and action taken regarding the study drug, corrective treatment, outcome, and investigator's assessment of causality. All AEs will be recorded and classified using terminology from the Medical Dictionary for Regulatory Activities (MedDRA). All reported treatment-emergent AEs (TEAEs), defined as any AE with an onset on or after the date of first study drug application, will be summarized by treatment group, the number of subjects reporting TEAEs, system organ class, preferred term, severity, and relationship to study drug. When summarizing TEAEs by severity or relationship to study drug, each subject will be counted only once within a system organ class or a preferred term using the event with the greatest severity or causality, respectively, within each category. All reported serious adverse events (SAEs) will be summarized by treatment group, the number of subjects

reporting SAEs, system organ class, preferred term, severity, and relationship to study drug.

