4.12.4 Subject randomization

At Visit 2, the investigator will determine the subject's eligibility for randomization to study medication. To be eligible for randomization the subject must:

- Continue to fulfill all the inclusion criteria and none of the exclusion criteria
- If a Woman of Childbearing Potential (WOCBP), has a negative urine pregnancy test result at Visit 1 and Visit 2
- Have clinical laboratory test results for all measured analytes at Visit 1 and all results are either within the range of normal for the laboratory or, any abnormal results, are defined as Not Clinically Relevant (NCR) by the investigator
- Have Visit 1 ECG results that are defined as Normal.

The investigator or designee will assign study medication to eligible subjects by selecting the Subject Kits in chronological sequence in ascending numerical order starting with the lowest available Subject Kit number. The investigator will not omit or reuse any Subject Kit number.

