5.2.5 Visit $6/Day \ge 36$ to ≤ 50 (Excision wound care)

This visit must occur 7 (± 4) days after Visit 5 and 7 (± 4) days prior to Visit 7.

At this visit, the investigator or designee will perform the following procedures:

- 1. Query the subject in a non-directive manner about any changes in her/his health since the previous visit and report any changes as medical history or report as an AE as appropriate
- 2. Query the subject about any changes in her/his concomitant therapies since the previous visit and report changes as appropriate
- 3. Confirm the subject has followed all study instructions
- 4. The investigator will manage the excision wounds per her/his standard of care
- 5. Review the study instructions with the subject
- 6. Schedule Visit 7.

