6.1.8 Electrocardiogram

A 12-lead ECG will be performed by a qualified investigational center staff member at the Visits 1, 2 (prior to randomization) and 5.

The ECGs must be obtained using a 12-lead ECG with a 10mm/mV amplitude, at 25mm/sec and 5-10 second duration. To ensure a steady heart rate the subject must rest quietly in the supine position for at least 5 minutes prior to performing the ECG.

The following parameter, at a minimum, will be determined:

- Heart rate
- RR interval
- PR interval
- QRS interval
- QT and QTc.

A normal ECG is defined as:

- QTc ≤450msec for males and ≤460msec for females (use of the ECG algorithm is acceptable for this purpose)
- Heart rate that is \geq 50 and \leq 100 beats/minutes
- The tracing must not show any:
 - o Rhythm disturbance other than a benign sinus dysrhythmia
 - Conduction disturbance including First Degree A-V Block (PR >200msec) and preexcitation (PR <120msec)
 - o Acute or chronic signs of ischemia.

Variations such as minor ST changes (*i.e.*, <0.5mm depression) and early re-polarization are considered normal.

The ECG results must be interpreted by a qualified health professional, the evaluator, and the interpretation reported either directly on the tracing or in a separate report. The evaluator and the investigator or designee may be the same person.

The investigator or a designee must review the ECG reports in a timely manner and in all cases prior to the next study visit. If an ECG result is defined as abnormal by the evaluator the investigator or designee should define the abnormality as CR or NCR. The investigator will record this information directly on the ECG tracing/report and date and initial the tracing/report.

The subject must not be randomized if the Visit 1 ECG is, in the evaluator's opinion, abnormal, regardless of the clinical relevance.

The investigator must report ECG results that are BOTH abnormal AND CR as medical history if found prior to the first study medication application or as an AE if found after the first study medication application begins.

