7.1 Definitions

7.1.1 Adverse Event (AE)

An AE is any untoward medical occurrence in a patient or clinical investigation subject administered a pharmaceutical product and which does not necessarily have a causal relationship with this treatment. An AE can therefore be any unfavorable and unintended sign or symptom associated with the use of an investigational product (including an abnormal laboratory finding), whether or not related to the investigational product.

Thus, any new, CR worsening of an existing sign, symptom or disease, should be considered an AE.

Worsening of the any Target cNF assessment should be reported as an AE only if the use of the study medication is interrupted or discontinued or other therapy is required to manage the event.

Every new episode or clinically relevant worsening of a chronic condition (*e.g.*, headaches, allergies, depression, and hypertension) should be reported as a separate AE, even if the condition is reported in the subject's medical history.

The investigator should, when certain, report a diagnosis rather than the signs, symptoms or clinically relevant abnormal laboratory values associated with the AE. Otherwise, signs, symptoms or abnormal laboratory values may be used to describe the AE.

An abnormality discovered (*e.g.*, clinically relevant laboratory abnormalities), prior to the first study medication application, should be reported as medical history, not as an AE.

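### A laboratory or ECG abnormality present before the first dose at Visit 2 but read afterwards must be reported as an AE and then counts as treatment-emergent; separately, the Visit 6 wording still permits filing as medical history.

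*Combined protocol and SAP*

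**What the plan says.** All references are to the combined protocol and SAP. The separate amendment changes only 8.3.3 and does not touch this point.

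- **Laboratory rule (6.1.2).** A result that is out of range and clinically relevant is reported "as medical history if found prior to the first study medication application or as an AE if found after" dosing has begun.
- **ECG rule (6.1.8).** "The investigator must report ECG results that are BOTH abnormal AND CR as medical history if found prior to the first study medication application". A finding noticed once dosing has started is an AE.
- **General AE definition (7.1.1).** An abnormality discovered "prior to the first study medication application, should be reported as medical history, not as an AE". Vital signs (6.1.6) follow the same pattern.
- **Sampling times (6.1.2).** Laboratory samples are taken at "Visits 1, 2 (prior to the randomization) and 5 (prior to the study medication application at the visit").
- **Condition for dosing (4.12.4).** Subjects must "Have clinical laboratory test results for all measured analytes at Visit 1", each normal or judged not clinically relevant, and a normal Visit 1 ECG. Section 5.2.2 likewise asks for review of Visit 1 results only.
- **Review deadlines.** Laboratory reports need timely review (6.1.2). ECG reports must be reviewed before the next visit at the latest (6.1.8).
- **TEAE (synopsis, Safety Analyses).** "defined as any AE with an onset on or after the date of first study drug application".
- **Synopsis laboratory rule (Safety Assessments).** An out-of-range, clinically significant result is an AE, with no exception for pre-dose samples.
- **Visit 6 (5.2.5, step 1).** The site asks about health changes and is told to "report any changes as medical history or report as an AE as appropriate".

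**The concern.** Whether an abnormality existed before treatment depends on when the sample or tracing was taken. The rule instead uses when someone noticed the result. The two can differ at Visit 2, where the pre-dose assessments and the first application share a day and nothing requires the Visit 2 results to be seen in between.

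AEs are a primary endpoint, and 8.3.4 describes a first-in-human study in which all AEs inform the safety profile unless obviously unrelated. The Visit 2 panel includes ALT, AST, bilirubin, creatinine and BUN, and 7.1.4 lists kidney and liver events as being of special interest. A misfiled pre-dose value could therefore land in a category that will be read closely. The same value is also the baseline for the shift tables, so an abnormality unchanged at Visit 5 would show no shift from baseline and still count as a TEAE.

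Visit 6 is a separate drafting problem in the opposite direction. It is the first scheduled visit after six excisions, and its wording permits a post-treatment health change to be recorded as medical history.

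**Working it through.** The plan states no figure on this point, so there is nothing to reproduce. The check is a comparison of rules, some visit-day arithmetic, and a calculation for scale.

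**1. Order of events at Visit 2 (5.2.2, steps for eligible subjects).** ECG is step 8, laboratory samples step 9, randomization step 10 and the first application step 13. The assessments precede dosing, and no step requires their results before step 13.

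**2. Classification when the result is read after step 13.** Under 6.1.2 and 6.1.8 the abnormality was found after the first application, so reporting it as an AE is mandatory. Under 7.1.1 it was not discovered before dosing, so the medical-history exception does not apply.

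**3. Treatment-emergent status.** The definition compares dates.
- Onset dated to the sample: Day 1 − Day 1 = 0 days, so it qualifies.
- Onset dated to the report: Day 1 or later, so it qualifies.
- Only an onset dated before Day 1 escapes. Section 8.3.4 plans a summary of pre-treatment AEs, but no rule sends a Visit 2 finding there.

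**4. Visit 6 against the AE window.** Visit 5 is 28 ± 4 days after Visit 2, so Day 25, 29 or 33. Under 7.2.1 AE reporting ends 30 days after the last application, which is given at Visit 5:
- 25 + 30 = Day 55
- 29 + 30 = Day 59
- 33 + 30 = Day 63

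Visit 6 is 3 to 11 days after Visit 5 (Day 28 to 44 overall), or Day 36 to 50 by the schedule. Both fall inside every window. Medical history is collected at Visit 1 and last updated at Visit 2 before randomization (6.1.4). Visits 3, 4, 5 and 7 ask for AEs only. The Visit 6 step repeats the pre-randomization instruction in 5.2.2, where a medical-history option makes sense.

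**5. Scale.** Let *p* be the probability that a subject has a clinically relevant abnormality in a Visit 2 pre-dose assessment that is first read after dosing. The documents give no value, so 1% to 10% is an assumption. Arm size *n* is 12 (48 subjects, synopsis) or 14 (56 subjects in 4.1 and 4.9; 56/4 = 14). With independent subjects, P(at least one in an arm) = 1 − (1 − *p*)^*n*.

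| *p* | *n* = 12 | *n* = 14 |
|---|---|---|
| 1% | 11% | 13% |
| 2% | 22% | 25% |
| 5% | 46% | 51% |
| 10% | 72% | 77% |

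Expected cases in the whole trial run from 0.01 × 48 = 0.48 to 0.10 × 56 = 5.6. One affected subject with no other TEAE moves the arm's rate by 1/12 = 8.3 points or 1/14 = 7.1 points.

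**The case against.** The best defence is that the Visit 2 path is conditional. It needs a new out-of-range value, a judgement of clinical relevance, a result first read after dosing, and an onset dated Day 1 or later. Screening removes subjects with clinically relevant laboratory results or an abnormal ECG at Visit 1. The late reading is itself an inference: the synopsis mentions a central laboratory, but no turnaround time is given. The ECG deadline is an outer limit, and a tracing may be read on site before dosing. All of this stands. It limits how often the error occurs, but the rule remains wrong when it does.

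A reader might infer that the rule biases the comparison of active gel with vehicle. The documents do not support that. The abnormality predates treatment and is classified under the blind, so the error is non-differential in expectation.

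A reader might also infer that the shift tables and TEAE tables flatly contradict each other. That is too strong. A value can be both baseline and AE, and the planned listings of out-of-range results and AE start dates would make the discrepancy traceable.

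On Visit 6, it is tempting to read 7.2.1 as making every event in its window an AE, or to conclude that events will be lost. Section 7.2.1 sets a reporting period only. Sections 6.3.3 and 7.1.1 exempt routine excision care and some Target tumor worsening. The Visit 6 text leaves the choice to the site's judgement, and 7.4 requires any AE in the period to be reported. No laboratory test or ECG is done at that visit. What remains is an internal contradiction that sites should not have to resolve.

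Finally, 8.3.1 defers detail to an SAP to be written before unblinding. That plan could settle the TEAE rule, but it would not correct what sites are told to enter as an AE.

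**Conclusion.** The point holds in limited form. Sections 6.1.2, 6.1.8 and 7.1.1 classify by time of discovery, so a pre-dose Visit 2 abnormality first read after dosing must be reported as an AE, and the calendar-date definition then makes it a TEAE. This is likely for laboratory samples if a central laboratory is used and less certain for ECGs. For vital signs the delay does not arise, because they are read at once before randomization.

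The consequence is noise in a primary safety endpoint, with no expected advantage to any arm. In arms of 12 or 14 the noise can be visible: a single subject is worth 8.3 or 7.1 points, provided that subject has no other TEAE. How often it would happen is unknown. The 11% to 77% range per arm depends entirely on the assumed 1% to 10% rate and on independence between subjects.

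The Visit 6 wording is a separate inconsistency with 6.1.4, 7.2.1 and Visits 3, 4, 5 and 7. It permits misfiling but does not require it.

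**What to change.** 1. In 6.1.2, 6.1.8 and 7.1.1, and in 6.1.6 for consistency, classify by whether the sample, tracing or measurement was taken before or after the first application. Remove the dependence on when the result was found or discovered.
2. Add the same pre-dose exception to the laboratory rule in the synopsis. Otherwise it will contradict the corrected sections.
3. In the TEAE definition, state that findings from Day 1 pre-application assessments are not treatment-emergent unless they worsen after the first application. If clock time is used, record the start time of the Visit 2 application as well, because 4.12.8 and 5.2.2 capture only its completion.
4. In 5.2.5 step 1, use the Visit 7 instruction, which asks for AEs only.

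The cost is small: wording in these sections and in the CRF guidelines, plus one CRF time field if clock time is chosen. No assessment or visit is added, and the order of procedures does not change.

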6.1.3 Local Tolerability Assessment

At Visits 2-5, the investigator and the subject will assess the local tolerability on each Target cNF using the LTA. The LTA is the investigator's and the subject's assessment of the average overall severity of the signs and symptoms, respectively, associated with irritation on each Target cNF. The investigator and subject must NOT refer to any other evaluation to assist with these assessments. This is not a comparison with the assessment at any other time point.

The investigator will assess the LTA for signs using the scales below:

Erythema			
0	None	No erythema present	
1	Mild	Slight red coloration	
2	Moderate	Definite redness	
3	Severe	Marked erythema, bright red to dusky dark red in color	

Edema		
0	None	No edema
1	Mild	Slight, but definite edema
2	Moderate	Definite edema
3	Severe	Marked edema

Scabbing/Crusting			
0	None	No scabbing/crusting	
1	Mild	Slight, but definite scabbing/crusting	
2	Moderate	Definite scabbing/crusting	
3	Severe	Marked scabbing/crusting	

Vesiculation		
0	None	No vesicles
1	Mild	Small vesicles, no pustules
2	Moderate	Vesicles with pustules, transudate may be present
3	Severe	Pustules with transudate, vesicles may be present, may extend outside treatment area

	Erosion			
0	None	No erosions		
1	Mild	Slight erosion on treatment area		
2	Moderate	Obvious erosion(s) on the treatment area		
3	Severe	Marked erosion that may extend outside treatment area		

The subject will assess the LTA for symptoms using the scales below:

Stinging		
0	None	No stinging
1	Mild	Slight stinging that is not bothersome
2	Moderate	Definite stinging that is somewhat bothersome
3	Severe	Intense stinging that causes definite discomfort and may interrupt daily activities and/or sleep

	Burning			
0	None	No burning		
1	Mild	Slight burning that is not bothersome		
2	Moderate	Definite burning that is somewhat bothersome		
3	Severe	Hot burning that causes definite discomfort and may interrupt daily activities and/or sleep		

	Pruritus			
0	None	No pruritus		
1	Mild	Slight pruritus that is noticeable but not bothersome		
2	Moderate	Definite pruritus that is bothersome but does not disrupt activities and/or sleep		
3	Severe	Intense pruritus that is bothersome and may interrupt daily activities and/or sleep		

The investigator will assess the LTA for signs according to the following schedule:

- At Visits 2 and 5, when a study medication application is performed at the investigational center, perform the LTA for each sign prior to the start of the study medication applications and 20 (±4) minutes after the Application Completion Time.
- At Visits 3, and 4, when no study medication application is performed at the investigational center, perform the LTA for each sign anytime during the visit.

The subject will assess the LTA for symptoms according to the following schedule:

- At Visits 2 and 5, when a study medication application is performed at the investigational center, perform the LTA for each symptom just prior to the start of the study medication applications and 10 (±4) minutes after the Application Completion Time
- At Visits 3 and 4, when no study medication application is performed at the investigational center, assess the LTA for each symptom over the previous 24 hours anytime during the visit.

Both the subject and the investigational center staff member will initial and date the source document to indicate the subject performed the LTA as instructed. The subject will mark the LTA grade for each symptom on each Target cNF on the appropriate source document. The staff member assisting the subject with the LTA assessment must not influence the subject's assessment.

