4.10 Subject instructions

At Visit 1, an investigational center staff member will dispense a Subject Instruction sheet to each subject.

During the entire duration of the study subjects must:

- Continue to use her/his routine cleansers and cosmetics
- Not apply any non-study topical products to any Target cNF within 18 hours prior to a study visit
- Avoid exposing each Target cNF to excessive natural (e.g., sunlight) or artificial (e.g., tanning beds) ultraviolet radiation and use her/his routine sunscreen if excessive exposure cannot be avoided
- Bring the subject instruction sheet to every visit.

During the 4-week treatment period, subjects must:

- Apply the study medication to each Target cNF as directed, once daily, with 24 (±6) hours between applications
- Not apply the study medication to any open wounds or obviously infected skin
- For Visits 3 and 4 do not apply the study medication within 18 hours prior to the visit
- Prior to Visit 5 perform the study medication application 24 (±6) hours prior to the visit
- Not wash or submerge a Target cNF Tumor for at least 6 hours after a study medication application
- Not apply any topical products to a Target cNF for at least 6 hours after a study medication application
- Not allow anyone else to use your study medication
- Keep the study medication away from children
- Store the study medication at room temperature
- Bring all study medication tubes to every visit
- Bring the subject instruction sheet to every visit.

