4.12.8 Study medication application

The study medications are for external, topical use on each Target cNF Tumor only and on the appropriate study subject only.

To perform a study medication application the subject should:

- Wash her/his hands before starting the application
- Avoid applying the study medication any open wounds or obviously infected skin
- Apply an amount of the assigned study medication sufficient to cover each Target cNF with a thin layer of the medication
- Gently rub in the study medication until no visible accumulation is evident
- Wash her/his hands after completing the application

The subject must apply study medication to the entire area of each Target cNF Tumor limiting exposure to the un-affected skin surrounding the tumor.

At Visit 2, an investigational center staff member will instruct the subject on the proper application technique. The staff member will observe the subject's study medication application to ensure proper application technique and record the time the subject completes the application to the last Target cNF Tumor as the Application Completion Time. The staff member will monitor the subject for adverse events for at least 20 minutes after the Application Completion Time. The subjects are to continue QD application of the assigned study medication to each Target cNF Tumor for 4 weeks with 24 (±6) hours between applications.

At Visit 5, the study medication application will be performed by the subject as part of the visit procedures at the investigational center. Record the time the subject completes the application to the last Target cNF Tumor as the Application Completion Time. The study medication tubes will be collected after the application at this visit.

For Visits 3 and 4 subjects should not apply the study medication within 18 hours prior to the study visit.

Prior to Visit 5 subjects must be instructed to perform the study medication application 24 (±6) hours prior to the visit.

After completing a study medication application, a subject should not:

- Wash or submerse any Target cNF Tumor for at least 6 hours
- Apply any topical products (*e.g.*, cosmetics, emollient/moisturizer, sunscreens) to any Target cNF Tumor for at least 6 hours.

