4.12.9 Dose Modification

Subjects should not modify the study medication application procedure or frequency. All application modifications must be reported on the appropriate CRF page.

If any significant study medication intolerance or safety issue occurs, after consulting with the NFlection's Medical Monitor, the investigator or designee may direct the subject to reduce the study medication application frequency. If the subject cannot perform QD applications to all Target cNF Tumors for more than 4 consecutive days, the subject must be removed from the study.

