5.2.3 Visits 3 and 4/Days 8 and 15 (QD Treatment)

These visits must occur within the following visit windows:

- Visit 3/Day 8: 7 days (±4 days) after Visit 2
- Visit 4/Day 15: 14 days (±4 days) after Visit 2.

Subjects should not apply the study medication within 18 hours prior to these study visits.

At these visits, the investigator or designee will perform the following procedures:

- 1. Query the subject in a non-directive manner about any changes in her/his health since the previous visit and report all AEs as appropriate
- 2. Query the subject about any changes in her/his concomitant therapies since the previous visit and report changes as appropriate
- 3. Confirm the subject has followed all study instructions
- 4. Confirm the location of each Target cNF Tumor
- 5. Have the subject perform an LTA of the symptoms for each Target cNF Tumor
- 6. The investigator will perform an LTA of the signs for each Target cNF Tumor
- 7. Collect and weigh study medication
- 8. Weigh and dispense study medication
- 9. Review the study instructions with the subject
- 10. Schedule the next study visit.

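### At Visits 3 and 4 the 24-hour symptom recall can contain no application of gel, so short-lived post-application symptoms may be missed

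*Combined protocol and SAP*

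**What the plan says.** All references are to the combined protocol and SAP.

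- **Symptom recall.** Section 6.1.3 has the subject grade stinging, burning and pruritus from 0 to 3 on each target tumor. At Visits 3 and 4 the instruction is to "assess the LTA for each symptom over the previous 24 hours anytime during the visit".
- **No dosing at the centre.** The same section describes these visits as ones without an application: "At Visits 3, and 4, when no study medication application is performed at the investigational center".
- **Hold before the visit.** Section 5.2.3: "Subjects should not apply the study medication within 18 hours prior to these study visits". Section 4.10 tells subjects the same: "For Visits 3 and 4 do not apply the study medication within 18 hours prior to the visit".
- **Interval between applications.** Section 4.10: "Apply the study medication to each Target cNF as directed, once daily, with 24 (±6) hours between applications".
- **Contrast with Visits 2 and 5.** At those visits subjects "perform the LTA for each symptom just prior to the start of the study medication applications and 10 (±4) minutes after the Application Completion Time" (section 6.1.3).
- **Timing before Visit 5.** Section 4.12.8: "Prior to Visit 5 subjects must be instructed to perform the study medication application 24 (±6) hours prior to the visit". Visits 3 and 4 have the 18-hour hold but no matching statement of how recent the last application must be.
- **Use of the data.** Safety and tolerability form a primary objective (section 2). Section 8.3.3 summarizes the tolerability items by treatment group and visit.

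**The concern.** The recall length and the dosing hold do not fit together. The hold sets a minimum of 18 hours since the last application, and the general interval rule allows up to 30. A fixed 24-hour recall falls inside that range, so two subjects who follow every instruction can answer different questions. One reports on a period that includes an application, and the other on a period that starts hours after it.

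Visits 3 and 4 supply the graded symptom data for Days 8 and 15. No application takes place there, so the recall is the only graded item that could pick up a reaction just after application on those days. If reactions are brief, whether they are recorded depends partly on the appointment time. The documents also do not ask for the time of the last application at these visits. Section 4.12.8 calls for an Application Completion Time only at Visits 2 and 5, and section 4.14 monitors frequency by questioning and tube weight. Empty windows therefore could not be identified afterwards.

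**Working it through.** The plan gives no figure on this point to reproduce. The check is interval arithmetic on its own times.

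**Inputs.** Recall of 24 h (section 6.1.3); hold of at least 18 h (sections 4.10, 4.12.8, 5.2.3); application interval of 24 ± 6 h, that is 18 to 30 h (sections 4.10, 4.12.8).

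**Range of the gap.** Let L be the hours from the last application to the visit.
- The hold gives L ≥ 18.
- The next application comes after the visit and at most 30 h after the last one, so L ≤ 30.
- The recall contains no application when L > 24. The part omitted after the last application is L − 24, at most 30 − 24 = 6 h.

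**When this occurs on a compliant schedule.** Let s be the hours from the subject's usual application time to the visit.

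| s | What the rules allow | L | Application in recall? |
|---|---|---|---|
| Above 0, up to 6 h | Hold the dose until after the visit, L = 24 + s. Moving it ahead of the hold in one step gives an interval of 6 + s = 6 to 12 h, below the 18 h minimum | above 24, up to 30 h | No |
| Between 6 and 12 h | Neither one-step option complies; the usual time must shift over more than one application | depends on the shift | Not determined |
| 12 to 18 h | Move the dose to 18 h before the visit, interval 6 + s = 18 to 24 h | 18 h | Yes |
| 18 to 24 h | Keep the usual time | 18 to 24 h | Yes |

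Example: usual application at 08:00, visit at 10:00. Then s = 2, L = 24 + 2 = 26 h, within the 30 h limit. The recall starts at 10:00 the day before and omits the first 26 − 24 = 2 h after application.

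**Share of empty windows.** The documents give no distribution for L, so each figure here is an assumption.
- L uniform on 18 to 30 h: (30 − 24)/(30 − 18) = 6/12 = 50%.
- L normal, truncated to 18 to 30 h (simulated):

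| Mean | SD 1 h | SD 2 h | SD 3 h |
|---|---|---|---|
| 20 h | 0% | 3% | 12% |
| 22 h | 2% | 16% | 28% |
| 24 h | 50% | 50% | 50% |
| 26 h | 98% | 84% | 73% |

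**Illustration of the effect on counts.** Take 12 subjects per arm (48/4, Synopsis) and assume that 30% have a symptom confined to the omitted period. The expected count is 12 × 0.30 = 3.6. With 25% of windows empty, 3.6 × 0.75 = 2.7 are recorded; with 50% empty, 3.6 × 0.50 = 1.8. A symptom that lasts into the recall period loses nothing.

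**Check of the remedy.** A recall running back to the last application contains exactly that application for every L from 18 to 30 h, so the empty share is 0%. A 48-hour recall does not do this. The second-last application lies 18 + 18 = 36 to 30 + 30 = 60 h before the visit, so 48 hours would cover one application for some subjects and two for others.

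**The case against.** The strongest reply is that Visits 3 and 4 may be meant to measure persisting irritation, with acute reactions left to Visits 2 and 5. Section 6.1.3 defines the assessment as average overall severity, not peak reaction, and nowhere ranks the minutes after application above other times. This reading is possible. It does not explain a 24-hour recall, though: the window takes in an application for some compliant subjects and not for others, so it measures neither persisting nor acute symptoms consistently.

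Several limits on the concern stand:

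- An empty window omits at most 6 hours, and often less. Longer-lasting symptoms, pruritus in particular, can still be reported.
- Only the three symptoms are affected. The five investigator-scored signs at Visits 3 and 4 do not depend on recall.
- A reader might infer that Visits 3 and 4 are the only tolerability assessments between the first and last application. They are not. Section 5.2.4 places symptom and sign scores at Visit 5 before the last application, with further scores after it.
- Visits 3 and 4 also carry a health query covering the time since the previous visit (section 5.2.3). It is non-directive and yields no 0 to 3 grade per tumor. Section 7.1.1 may narrow it further, since worsening of a target tumor assessment counts as an adverse event only if treatment is interrupted or stopped or other therapy is needed. The text does not clearly say whether that covers stinging or itch.

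A reader might also infer that differences between gel strengths are hidden. The documents do not support that. The rules are identical in all arms and do not by themselves favor one, and acute differences remain observable at Visits 2 and 5. Lower recorded frequencies could shrink a difference, but this is not shown. One route to uneven loss exists: for intolerance, after consultation with the sponsor's medical monitor, "the investigator or designee may direct the subject to reduce the study medication application frequency" (section 4.12.9). That would lengthen the gap in the affected subjects. Whether it would differ by arm cannot be known from the documents.

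**Conclusion.** The point holds in a limited form. A fully compliant subject can reach Visit 3 or 4 with no application in the 24-hour symptom recall, and an ordinary schedule produces this: a morning application and a visit later that morning. Brief stinging, burning or pruritus after application may then be missed at these two visits, and appointment time decides for whom.

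It would go too far to say that mid-treatment symptoms are under-counted. That needs symptom durations and application times, and the documents give neither. The 50% share rests on an assumed uniform gap. The range of about 0% to 98% shows how far the answer moves with the assumed timing, and nothing in the documents favors either end. The interval arithmetic rests only on the stated hold, interval and recall. The change is worth making because it is cheap and the data serve a primary objective.

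**What to change.** In section 6.1.3, change the Visit 3 and 4 symptom recall from the previous 24 hours to *since, and including, the most recent study medication application*. Add the date and time of that application to the source form at these two visits. Check sections 4.10, 4.12.8, 5.2.3 and 6.1.3 against each other so that the recall and the stated timing agree. Leave the application timing unchanged.

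The cost is a wording change and one extra source-form field. The downside is a recall that varies slightly in length between subjects, from 18 to about 30 hours on a compliant schedule. The recorded time lets the analysis describe that variation. It also shows any gap beyond 30 hours, for instance after a reduction in application frequency.
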